7.3 Study Hypotheses

- Among PWID at elevated risk for treatment failure, PWID receiving the high intensity intervention will have significantly higher SVR than those receiving either the medium or low intensity interventions.
 - 1a. Among PWID at minimal risk of treatment failure, PWID receiving either the high or medium intensity intervention will have significantly higher SVR than those receiving the low intensity intervention.
- 2. Among PWID at elevated risk for treatment failure, PWID receiving the high intensity intervention will have significantly higher treatment completion than those receiving either the medium or low intensity interventions.
 - 2a. Among PWID at minimal risk of treatment failure, PWID receiving either the high or medium intensity intervention will have significantly higher treatment completion than those receiving the low intensity intervention.
- 3. Among PWID at elevated risk for treatment failure, PWID receiving the high intensity intervention will have significantly higher adherence than those receiving either the medium or low intensity interventions.
 - 3a. Among PWID at minimal risk of treatment failure, PWID receiving either the high or medium intensity intervention will have significantly higher adherence than those receiving the low intensity intervention.
- 4. HCV reinfection rates will be lower among clients who have high engagement with OAT.

5. Among HIV/HCV co-infected PWID, HIV viral suppression will be higher after achievement of HCV cure.

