8.2 Secondary Objective(s)

- 1. To evaluate whether the intensity of treatment adherence support affects HCV treatment completion rates.
- 2. To evaluate whether the intensity of treatment adherence support affects HCV treatment adherence.
- 3. To estimate the incidence and correlates of HCV reinfection among HCV mono- and HIV/HCV coinfected PWID who achieve HCV cure.
- 4. To evaluate the impact of HCV cure on HIV viral suppression among HIV/HCV coinfected PWID.

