15.3.2. Secondary objectives / hypotheses

15.3.2.1. To evaluate whether the intensity of treatment adherence support affects HCV treatment completion rates.

Hypothesis: Among PWID at elevated risk for treatment failure, PWID receiving the high intensity intervention will have significantly higher treatment completion than those receiving either the medium or the low intensity interventions.

Hypothesis: Among PWID at minimal risk for treatment failure, PWID receiving either the high or the medium intensity intervention will have significantly higher treatment completion than those receiving the low intensity interventions.

15.3.2.2. To evaluate whether the intensity of treatment adherence support affects HCV treatment adherence.

Hypothesis: Among PWID at elevated risk for treatment failure, PWID receiving the high intensity intervention will have significantly higher adherence than those receiving either the medium or the low intensity interventions.

Hypothesis: Among PWID at minimal risk of treatment failure, PWID receiving either the high or the medium intensity intervention will have significantly higher adherence than those receiving the low intensity intervention.

15.3.2.3. To estimate the incidence and correlates of HCV reinfection among HCV mono- and HIV/HCV coinfected PWID who achieve HCV cure.

Hypothesis: HCV reinfection will be lower among clients who have higher attendance at OAT programs.

15.3.2.4. To evaluate the impact of HCV cure on HIV viral suppression among HIV/HCV coinfected PWID.

Hypothesis: Among HIV/HCV co-infected PWID, HIV viral suppression will be higher after achievement of HCV cure.

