Reinfection (secondary outcome). Reinfection will be defined as testing positive for HCV Core Ag after achieving SVR. This may be at any of the post SVR follow-up visits. To evaluate factors independently associated with reinfection, all clients who achieve SVR and have at least one subsequent HCV Core Ag assessment will be included. Using survival analysis, factors associated with reinfection will be assessed. These including ongoing substance use, needle sharing, OAT, SSP use, HIV status and frequency of visits to the ICC. We will also evaluate whether the risk stratum or intervention had impact on reinfection outcomes as well as the reinfection rate over time elapsed since treatment completion. In order to account for missing data due to loss-to-follow-up, we will use inverse-weighting methods.^{97,98}

HIV viral suppression (secondary outcome). Annual assessments of HIV viral load among HIV/HCV coinfected participants in the 7 ICCs are expected as part of other ICC activities and standard of care at Indian government ART centers. All available viral load measurements for HIV/HCV co-infected PWID enrolled in the trial will be used. Viral suppression will be defined as HIV RNA <LLOQ. We will compare viral suppression across two groups defined by primary outcome status, which will be cured vs. not cured using logistic regression with generalized estimating equations (GEE) to account for repeated measures within individuals. All potentially confounding factors known to be associated with HCV cure and HIV viral suppression in this population including demographics, substance use, needle sharing, OAT, SSP use, social support and frequency of visits to the ICC will be accounted for. Analyses will be combined across all groups but we will include a covariate for the classification of risk of treatment failure (minimal or elevated). To evaluate whether the intensity of HCV treatment support also had any impact on HIV viral suppression outcomes, a covariate for the intensity of intervention received will also be included. In order to account for missing data due to loss-to-follow-up, we will use inverseweighting methods. 97,98 Additional sensitivity analyses will vary the threshold for HIV viral suppression to account for blips, considering cutoffs of <200 copies/ml, <500 copies/ml and <1000 copies/ml.

15.7.2.3. Exploratory analysis.

Exploratory outcomes. These are described in the Statistical Analysis Plan.

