2b.3. Subgroup analyses. Subgroup analyses will explore whether the effect of the intervention in either risk stratum varies by the prognostic score itself as well as by other covariates of interest including age, employment status, HIV status and treatment, drug use, injection drug use, alcohol use, homelessness, depressive symptoms, medication for opioid use disorder (MOUD), distance to study site, readiness for HCV treatment and study site. Interactions will be included in regression models that also adjust for site.

2c. Reinfection.

In the primary analysis, reinfection will be defined as testing positive for HCV Core Ag after achieving SVR. This may be at any of the post SVR follow-up visits. To evaluate factors independently associated with reinfection, all clients who achieve SVR and have at least one

subsequent HCV Core Ag assessment will be included. Reinfection rate per 100 person years will be calculated. Using survival analysis, factors associated with reinfection will be assessed. These including ongoing substance use, needle sharing, MOUD, SSP use, HIV status and frequency of visits to the ICC. We will also evaluate whether the risk stratum or intervention had impact on reinfection outcomes as well as the re-infection rate over time elapsed since treatment completion. In order to account for missing data due to loss-to-follow-up, we will use inverse-weighting methods.^{4,5}

2c.1. Sensitivity analyses. Analyses will be repeated using a reclassified reinfection outcome that incorporates sequence analysis (to reclassify samples at SVR as treatment failures vs. reinfection).

2d. HIV viral suppression.

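### The hypothesis that OAT attendance lowers HCV reinfection has no model of its own, and the only planned analysis, read naturally, would adjust away part of the effect

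*SAP*

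**What the plan says.** The hypothesis is directional and appears twice. Protocol 7.3 has "HCV reinfection rates will be lower among clients who have high engagement with OAT"; protocol 15.3.2.3 has "HCV reinfection will be lower among clients who have higher attendance at OAT programs". Neither engagement nor attendance is defined. The objective above it (protocol 8.2) is descriptive: "To estimate the incidence and correlates of HCV reinfection among HCV mono- and HIV/HCV coinfected PWID who achieve HCV cure".

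One analysis covers this, in nearly the same words in protocol 15.7.2.2 and SAP 2c. Its stated purpose is to find "factors independently associated with reinfection", and the method is given as "Using survival analysis, factors associated with reinfection will be assessed". The SAP then lists the factors: "These including ongoing substance use, needle sharing, MOUD, SSP use, HIV status and frequency of visits to the ICC". The protocol's list is the same with OAT in place of MOUD: "These including ongoing substance use, needle sharing, OAT, SSP use, HIV status and frequency of visits to the ICC". Neither document names OAT as the exposure of a dedicated model, gives an adjustment set, or says whether covariates are fixed or time-updated.

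**The concern.** The hypothesis asks whether people who attend OAT more are reinfected less. The expected route is less injecting and less sharing. A model that holds current use and sharing constant asks something else: whether OAT lowers reinfection among people whose use and sharing are already the same. If OAT works mainly through behaviour, the answer to that second question is close to no effect even when OAT protects.

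Visit frequency adds a separate problem. OAT is dispensed through the ICCs, with doses observed seven days a week or, under COVID-era arrangements at most ICCs, extended dosing, mostly seven days of medication per visit (protocol 11.1.1.3). The number of ICC visits is therefore partly a count of OAT attendance.

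At stake is the answer to a stated secondary hypothesis with programme consequences. The randomised comparisons and the primary endpoint are not affected.

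**Working it through.** The documents give no reinfection rate, OAT effect, event count or power for this hypothesis, so there is no figure of the plan's own to reproduce. The check shows direction, and size only under stated assumptions.

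**From the documents**

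- Use and sharing are recorded at entry, on treatment, at the SVR visit and at every post-SVR visit (protocol 12.3.10), so values from after OAT exposure will be available.
- OAT coverage among ICC clients runs from 0% (Kanpur) to 74.4% (Ludhiana) in Table 10.1. Weighted by clients it is 569,941/11,293 = 50.5, that is 50.5%.

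**Simplest case (assumed rates).** Sharing 40% off OAT and 20% on OAT; reinfection 10 per 100 person-years with sharing and 1 without.

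- Off OAT: 0.4 × 10 + 0.6 × 1 = 4.6
- On OAT: 0.2 × 10 + 0.8 × 1 = 2.8
- Total rate ratio: 2.8/4.6 = 0.61. Within each sharing group the rates are equal, so the adjusted ratio is 1.00.

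**Use and sharing together (assumed).** OAT lowers ongoing use from 60% to 35%. Use triples the rate. Sharing (35% of users, 2% of non-users) doubles it. OAT also has a direct rate ratio *d*.

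- Relative rate, users: 3 × (0.65 × 1 + 0.35 × 2) = 4.05
- Relative rate, non-users: 0.98 × 1 + 0.02 × 2 = 1.02
- Off OAT: 0.60 × 4.05 + 0.40 × 1.02 = 2.838
- On OAT: *d* × (0.35 × 4.05 + 0.65 × 1.02) = *d* × 2.0805
- Total ratio: *d* × 2.0805/2.838 = *d* × 0.733

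A simulation on these assumptions (Poisson rates, 600,000 people, 1.5 years each, about half on OAT) gave:

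| Scenario | Total OAT rate ratio | Adjusted for ongoing use and sharing |
|---|---|---|
| *d* = 1.0 (full mediation) | 0.73 | 1.00 |
| *d* = 0.8 | 0.59 | 0.80 |
| *d* = 0.6 | 0.44 | 0.61 |
| *d* = 1.0, plus an unmeasured cause of use and reinfection | 0.79 | 1.10 |

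**Power (assumed event counts).** Power = Φ(|ln HR| × √(D × 0.53 × 0.47) − 1.96), with D events and 53% on OAT.

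- D = 150: HR 0.59 gives Φ(0.528 × 6.11 − 1.96) = 90%; HR 0.80 gives Φ(0.223 × 6.11 − 1.96) = 28%.
- D = 250: 99% and 42%.
- Full mediation: HR 0.73 gives 49% (D = 150) or 70% (D = 250); at HR 1.00 only the nominal error rate remains.

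**When baseline severity also confounds.** Severity is assumed to raise ongoing use and to change the chance of being on OAT; *d* = 1.0.

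| Who takes OAT | True | Crude | Adjusted for baseline severity | Adding ongoing use and sharing |
|---|---|---|---|---|
| Heavier users less often | 0.76 | 0.65 | 0.74 | 0.98 |
| Heavier users more often | 0.76 | 0.87 | 0.75 | 0.99 |

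The crude ratio is wrong in either direction. Adjustment for severity before exposure comes close to the truth, and adding ongoing behaviour removes the effect.

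**The case against.** The strongest reply is that the faulty model is not written down. SAP 2c lists candidate factors and never says they are adjusted for together, whereas SAP 2d states outright that its analysis is adjusted for a similar set as confounders. A reader might infer that the SAP commits to judging OAT in one model containing its mediators; the text does not say so. It is an inference from the word *independently* and from *ongoing* as the description of substance use. The inference is natural, and on any other reading the hypothesis still has no specified test.

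The mediator role is likewise subject-matter reasoning. The nearest text, protocol 7.1.6, says only that modelling supports harm reduction alongside treatment as a way to lower reinfection risk. Covariate timing is open too: use and sharing measured before the OAT window would be confounders, and adjusting for them would be right. Because current use can also drive attendance, dropping these variables altogether is no remedy, as the crude ratios of 0.65 and 0.87 show. All of this stands, and it shapes the fix.

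It can also be said that the objective promises only correlates. That is true of protocol 8.2, but 7.3 and 15.3.2.3 add a directional statement about OAT that a list of correlates does not test.

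**Conclusion.** The point holds as a specification gap with a predictable consequence. The OAT hypothesis has no model of its own, and the natural reading of the one planned analysis would attenuate the OAT estimate. The direction rests on two assumptions: that use and sharing lie on OAT's path to reinfection, and that their values are taken after the OAT exposure.

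The size cannot be derived from the documents. Under the assumed rates, full mediation takes 0.61 or 0.73 to 1.00, while partial mediation takes 0.59 to 0.80 or 0.44 to 0.61. A reader might infer that a real OAT benefit would be reported as absent. That follows only under full or nearly full mediation, or with too few events to detect the attenuated ratio, and the documents establish neither. The weight is moderate: the analysis is secondary and observational, but the correction is cheap and the data are already being collected.

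**What to change.** In SAP 2c, pre-specify a separate model for this hypothesis:

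- **Exposure:** OAT attendance over the visit interval preceding each core-antigen test, from the daily MOUD records described in SAP 3a, with attendance defined.
- **Adjustment:** site, and confounders measured before that interval: injecting and sharing before the interval, age, HIV status, housing, risk score and prior OAT. Site is needed because OAT coverage runs from 0% to 74.4%. Prior OAT is needed because in six of the seven sites 25.2% to 74.4% of clients were on OAT in Table 10.1, so entry behaviour may already reflect it.
- **Left out:** same-interval substance use, needle sharing and ICC visit frequency.
- **Sensitivity analysis:** a marginal structural (inverse-probability-weighted) model, because use and sharing can be both confounder and mediator over time.
- **Correlates:** keep the mutually adjusted model, labelled as a description of correlates and not as the test of the OAT hypothesis.

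The cost is SAP wording and slightly more analysis, with no new data collection. The OAT estimate remains observational.

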^{*}For participants who receive 24 weeks of therapy, the SVR visit will take place at 36 weeks

^{**}For participants who receive 24 weeks of therapy, these visits will take place at weeks 60, 84, 108, 132, 156, 180, 204, 228

^{***}Additional doses will be observed for Arm 3 (36 to 84 for those receiving 12 weeks of treatment and 72 to 168 for those receiving 24 weeks)

^{****}Only assessed on participants who achieve HCV cure

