Annual assessments of HIV viral load among HIV/HCV coinfected participants in the 7 ICCs are expected as part of other ICC activities and standard of care at Indian government ART centers. All available viral load measurements for HIV/HCV co-infected PWID enrolled in the trial will be used. Viral suppression will be defined as HIV RNA less than LLOQ. We will compare viral suppression across two groups defined by primary outcome status, which will be cured vs. not cured using logistic regression with generalized estimating equations (GEE) to account for repeated measures within individuals. Because these groups will be defined by the primary outcome and no longer balanced by randomization, analysis will be adjusted for confounding factors including demographics, substance use, needle sharing, MOUD, SSP use, social support and frequency of visits to the ICC. Analyses will be combined across all groups but we will include a covariate for the classification of risk of treatment failure (minimal or elevated) and intervention received. In order to account for missing data due to loss-to-follow-up, we will use inverse-weighting methods.^{4,5}

2d.1. Sensitivity analyses. We will vary the threshold for HIV viral suppression (<150 copies/ml vs. 400 copies/ml vs. 1000 copies/ml) and will also incorporate the revised definition of SVR vs. treatment failure using sequence data.

3. Exploratory analysis

3a. Impact of interventions on medication for opioid use disorder (MOUD) utilization. Daily MOUD utilization data is available in the electronic health record. We will explore the impact of the interventions within strata by arm on new MOUD initiation and MOUD retention using methods of survival analysis, logistic regression with GEE and growth mixture models. Analyses will be adjusted for site. Additional sensitivity analyses will be similar to those reported in the primary and secondary outcome analyses and will include accounting for the prognostic score.

3b. Impact of interventions on quality of life.

Quality of life data is captured at the SVR visit and at semi-annual post-treatment follow-up visits. Using logistic and linear regression with GEE, we will explore the impact of interventions within strata on quality of life after treatment.

3c. Impact of interventions on mortality.

Using Poisson regression, we will explore the impact of interventions within strata on all-cause mortality.

3d. Effect of delays in treatment completion on SVR.

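### The arm contrast on reinfection in SAP 2c is made only among cured participants, so it is not a randomized comparison and should be labelled descriptive, with an all-randomized analysis added

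*SAP*

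**What the plan says.** SAP 2c sets the outcome: "reinfection will be defined as testing positive for HCV Core Ag after achieving SVR". The analysis set in Protocol 15.7.2.2 is: "all clients who achieve SVR and have at least one subsequent HCV Core Ag assessment will be included"; SAP 2c has the same rule. Under the schedule in Protocol 12.1, core antigen is "Only assessed on participants who achieve HCV cure".

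Within that set SAP 2c looks for factors associated with reinfection (substance use, needle sharing, MOUD, syringe services, HIV status, clinic visits). It then turns to arm: "We will also evaluate whether the risk stratum or intervention had impact on reinfection outcomes".

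Two further provisions accompany this. One is weighting: "In order to account for missing data due to loss-to-follow-up, we will use inverse-weighting methods". The other, in 2c.1, concerns outcome classification: "Analyses will be repeated using a reclassified reinfection outcome that incorporates sequence analysis".

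SAP 2d, on HIV suppression by cure status, does recognise the issue: "Because these groups will be defined by the primary outcome and no longer balanced by randomization, analysis will be adjusted for confounding factors". SAP 2c has no such statement. SAP 3e plans average treatment effects for SVR and for the secondary outcomes, of which reinfection is one. The corresponding text in Protocol 15.7.2.3 names only SVR and treatment completion.

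**The concern.** Protocol 15.3.1 hypothesizes that, in the elevated-risk stratum, high-intensity support raises SVR over medium and low. If it does, the cured group in the high arm contains people who would not have been cured with less support, and the cured group in the low arm has no counterpart to them. Any difference in their underlying reinfection risk then enters the arm contrast, even if support has no effect on reinfection. Requiring a later core antigen test adds a second selection after randomization.

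A link between curability and reinfection risk is plausible. The preliminary failure-risk model in Protocol 15.5 uses injection frequency and OAT use, and SAP 2c lists substance use, needle sharing and MOUD as candidate reinfection factors.

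What is at stake is one secondary conclusion. A programme could read a rate ratio above 1 as harm from support, or one below 1 as protection, when the ratio reflects only who was cured.

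**Working it through.** **What the provisions in 2c cover.** The inverse weighting addresses loss to follow-up. The 2c.1 sensitivity analysis addresses misclassification. The weights in SAP 3e remove the link between prognostic score and arm. None addresses selection into cure.

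**Inputs from the documents (Protocol 15.4, elevated-risk stratum of 1,500).** 750 high and 250 low; comparator SVR 0.85; detectable RR, high versus low, 1.08; two-sided alpha 0.05; 80% power. The documents give no reinfection rate, event count or power for reinfection.

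**Reproducing the plan's figure.** A pooled two-proportion test with 250 versus 750 and SVR 0.85, solved at 80% power, gives RR 1.0755, which rounds to the stated 1.08. The high-arm SVR used below is 0.85 × 1.08 = 0.918.

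**Bounding case, no true effect on reinfection.** Assume everyone cured with low support would also be cured with high support, and that all extra cures are reinfected k times as fast as the rest.
- Extra cures as a share of the high arm's cured: f = (0.918 − 0.85)/0.918 = 0.0741.
- Spurious rate ratio, high versus low: 1 + f(k − 1).
- k = 2: 1.07; k = 3: 1.15; k = 5: 1.30.
- If the extra cures are at lower risk, say k = 0.5: 1 − 0.0741 × 0.5 = 0.96, so the sign turns.

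This formula gives everyone equal person-time. If person-time ends at reinfection (base rate 5 per 100 person-years, assumed), the ratio over T years is [0.85(1 − e^(−0.05T)) + 0.068(1 − e^(−0.05kT))] / [0.85(1 − e^(−0.05T)) + (0.068/k)(1 − e^(−0.05kT))]. For k = 5 this is 1.27 at 1 year and 1.24 at 2.5 years.

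**Milder case.** Assume 30% of participants are unstable and that stable participants have SVR 0.95 in both arms.
- Unstable SVR, low arm: (0.85 − 0.7 × 0.95)/0.3 = 0.617. High arm: (0.918 − 0.665)/0.3 = 0.843.
- Unstable share among the cured: 0.185/0.85 = 0.218 (low); 0.253/0.918 = 0.276 (high).
- Spurious ratio: [1 + 0.276(k − 1)]/[1 + 0.218(k − 1)] = 1.05, 1.08 and 1.12 for k = 2, 3 and 5.

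With equal SVR and equal case mix the ratio is 1.00.

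**False-positive rate, one example.** Cured: 750 × 0.918 = 688.5 and 250 × 0.85 = 212.5, a low-arm share of 0.236. Take the bounding ratio for k = 3, an assumed 10 per 100 person-years and 2.5 years. Events = 901 × 2.5 × 0.10 = 225. The mean of the test statistic is √(225 × 0.236 × 0.764) × ln 1.148 = 0.88, so a nominal 5% test rejects a true null about 14% of the time. Over k = 2 to 5, 5 to 20 per 100 person-years and 1 to 2.5 years, the range is about 5.5% to 65%. The top is overstated because person-time here does not stop at reinfection.

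**The two questions can disagree.** Use the milder mix with k = 3, 5 per 100 person-years in stable participants, and 2 years. Virus-free among all randomized is 0.665e^(−0.1) + 0.185e^(−0.3) = 73.9% (low) and 0.665e^(−0.1) + 0.253e^(−0.3) = 78.9% (high). Reinfected among the cured is 1 − 0.739/0.85 = 13.1% (low) and 1 − 0.789/0.918 = 14.0% (high). The cured-only contrast looks worse for high support, while more of that arm remains virus-free.

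**The case against.** The declared objective is the incidence and correlates of reinfection among people who are cured, and the only reinfection hypothesis concerns OAT (Protocol 15.3.2.3). For that purpose the cured are the right population. Arm appears in one clause, next to risk stratum, which is not randomized either. All of this stands and limits the scope: the fault lies in reading the arm coefficient as an effect of the intervention.

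A reader might infer that high-intensity support will look as if it causes reinfection. The documents do not support that. Being cured only with more support implies failure with less, not faster reinfection. The nearest data, the team's earlier trial in Protocol 7.1.8, found no difference in completion or SVR by ongoing drug use in its 12-week arm. That trial had 50 participants, all on DOT, so it does not settle the matter, but the direction remains an assumption.

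A reader might also infer that no overall-population analysis is foreseen. SAP 3e does plan average treatment effects for the secondary outcomes. It does not say how an outcome that exists only after SVR would be handled, so it does not close the gap. Likewise, the correlates in 2c might absorb part of the bias, but the text does not say that the arm term is adjusted for them, and several may be measured after randomization.

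**Conclusion.** The point holds as a limited one. The planned arm contrast on reinfection is conditioned on the primary outcome, and the plan neither says so nor corrects for it, although SAP 2d states the principle for a neighbouring analysis. A spurious effect needs two things: arms that differ in who is cured, and extra cures whose reinfection risk differs from the rest. At the design's SVR contrast the distortion is modest unless the extra cures are reinfected several times as fast. The multipliers, the unstable share and the reinfection rates are all assumptions. The primary SVR analysis, reinfection incidence among the cured and the OAT hypothesis are untouched.

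**What to change.** 1. In SAP 2c, keep the cured-only survival model for incidence and correlates. State that its arm coefficient is descriptive and is not an effect of the intervention. In 3e, exclude this cured-only contrast from the average treatment effects.
2. For the effect of support, add a within-stratum analysis of all randomized participants. The outcome is SVR and no later positive core antigen by a fixed time from randomization, with non-SVR or reinfection as failure. Use Kaplan-Meier or the already planned inverse weighting for incomplete post-SVR follow-up. Core antigen in the uncured is not needed, because they already count as failures.
3. Set the fixed time so that a participant whose SVR is confirmed at the end of the window could still have one later core antigen visit. The window ends at week 12 + 60 = 72, or 24 + 60 = 84 for 24-week regimens, so week 72 is too early. Adding the 24-week visit interval and the 4-week visit window gives 72 + 28 = 100 and 84 + 28 = 112.

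The cost is SAP wording and one extra analysis on data already collected. There are two downsides. Late enrollees will be censored before the fixed time; Protocol 15.6 allows that some have no post-SVR follow-up at all. The composite also measures remaining virus-free, which is driven largely by SVR, and does not isolate reinfection.
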